### **Efficacy evaluation:**

The primary outcome measure will be the change from baseline using the Zanarini Rating Scale for Borderline Personality Disorder (“Zanarini scale”) (45). This semistructured interview has anchored ratings (0=no symptoms, 4=severe symptoms) on nine items that correspond to the DSM-5 BPD criteria. Its subscales will be considered secondary efficacy measures.

Secondary efficacy measures include Modified Overt Aggression Scale (46), the Young Mania Rating Scale (47), and the self-report version of the Zanarini scale (48), the Borderline Evaluation of Severity Over Time (49), the Barratt Impulsiveness Scale (50) the Minnesota Impulsive Disorders Interview (51), the Symptom Checklist–90–Revised (SCL-90-R) (52), and the scales listed above (41-44).

### *Cognitive Measures*

Cognitive assessments consist of two previously validated tests taken from CANTABeclipse software. The choice of cognitive challenges was based on the clinical features of BPD. The order of the tasks will be fixed and participants will complete the tasks at first visit (baseline), midway through 13-week timeline, and endpoint.

Cognitive flexibility, i.e., set-shifting, will be measured using the Intra-dimensional/Extra-dimensional Shift Task (ID/ED task). Participants are presented with two stimuli on-screen for each trial and attempted to learn an underlying ‘rule’ about which stimulus was correct. Key outcome measures will be number of errors made at the intra-dimensional shift and at the extra-dimensional shift stage.

The Tower of London task will be used to examine executive planning. On each trial of the task, subjects observe two sets of pockets each containing three colored balls on-screen. On ‘move’ trials, subjects have to attempt to work out ‘in mind’ the minimum number of moves required to move the balls in one set of pockets to match a goal arrangement also shown in the other set of pockets.

The probabilistic beliefs task will allow us to examine the subject’s self-other distinction. Participants observe a sequence of neutral images on the screen and are occasionally asked to

make responses on a keyboard. Participants will be asked to keep track of the images they see and make predictions about what will happen next. They will also be asked to keep track of another theoretical person's beliefs about what will happen next. The task will allow us to submit self-other distinctions, a potentially important dimension of BPD, to quantitative assessment and computational modelling.

### *Subject Withdrawal*

If a subject withdraws from the study, all instruments administered at the screening visit will be completed at the final visit. These will be conducted when the subject is able to come in for an early termination visit. Withdrawn subjects will be given the phone number of the principal investigator as well as the phone numbers of local resources for depression treatment.

### *Safety Assessments*

Safety and tolerability will be assessed using spontaneously reported adverse events data, C-SSRS, vital signs, and by evaluating premature termination. Safety assessments (sitting blood pressure, heart rate, adverse effects, and concomitant medications) will be documented at each visit. Subjects who are an immediate suicide risk will be removed from the study and appropriate clinical intervention (e.g. hospitalization) will be arranged. Study team members are mandated reporters and as such, will arrange for the subject to be taken to the emergency room if any intent to harm themselves is expressed. Urine pregnancy tests will be performed at the initial visit. Subjects who have a positive urine pregnancy test will be excluded from the study. Assessment of side effects will be done at each visit.

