**Objective**

The primary objective of the proposed study is to evaluate the safety and efficacy of Brexpiprazole in adults with borderline personality disorder (BPD). Eighty subjects with BPD will be randomized in a 1:1 fashion to either Brexpiprazole (starting at 1mg/day for one week and going to 2mg in a fixed dose fashion after 1 week) or matching placebo for 12 weeks of active treatment. The hypothesis to be tested is that Brexpiprazole will result in greater rates of reduction in symptoms of BPD compared to placebo (improvement in symptoms will be indicated by lower scores on established outcome measures of BPD symptoms that have been used in prior studies).

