#### *Assessments at each visit*

Those subjects who appear appropriate for the study, based on telephone screening, will be invited for a baseline assessment. The duration of the baseline assessment will be approximately 90 minutes and will include the following: Informed consent, Demographic data, Concomitant medications (no psychotropic medications will be allowed), Family history data, Medical evaluation including physical examination, EKG, weight, and vital signs, Urine pregnancy test (for women of childbearing years) and urine drug screen, and a psychiatric evaluation (using the following measures: MINI International Neuropsychiatric Interview (40); Depressive symptoms will be rated with the 24-item Hamilton Depression Rating Scale (HAM-D) (41); Anxiety

symptoms will be assessed using the Hamilton Anxiety Rating Scale (HAM-A) (42); Psychosocial functioning will be evaluated using the patient-rated version of the Sheehan Disability Scale (SDS) (43); Quality of Life Inventory (QOLI) (44); The Cambridge-Chicago Compulsivity Trait Scale (CHI-T); and the Columbia Suicide Severity Rating Scale (C-SSRS)). During the consent process, individuals will be given time to review the consent form and given the opportunity to ask any questions that may arise before signing the informed consent form. Throughout the study, subjects will be asked questions about the study to ensure that they continue understanding study procedures. Blood samples will be collected at both baseline and last visits to measure blood sugar, glutathione, and cholesterol levels. All follow-up visits will include safety measures (adverse events, vital signs, C-SSRS), weight, BPD measures, and other psychiatric measures.

Due to the pandemic of COVID19, study participants can perform their baseline and follow-up visits online using encrypted Zoom instead of in person visits. All inventories will be assessed. Blood samples and urine toxicology, however, will be at the discretion of the study PI. In cases where they are considered medically necessary, the participant can have them drawn locally and submitted to the study team.

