### *Risks of Brexpiprazole*

The most common side effects associated with Brexpiprazole include:

- Weight gain
- Inner sense of restlessness (feeling like one needs to move)

Brexpiprazole may cause more serious side effects including:

- Stroke in elderly people
- Neuroleptic Malignant Syndrome (high fever, stiff muscles, sweating, changes in pulse, heart rate and blood pressure)
- Tardive dyskinesia (uncontrollable body movements)
- High blood sugar
- Low white blood cell count
- Decreased blood pressure
- Seizures
- Problems controlling your body temperature so that the individual feel too warm
- Difficulty swallowing that can cause food or liquid to get into the lungs

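### Safety is part of the primary objective, but the stated method for finding adverse events is spontaneous report, and nothing is directed at the restlessness and abnormal movements the protocol lists, so these may be under-counted

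*Combined protocol and SAP*

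**What the plan says.** The Objective section opens: "The primary objective of the proposed study is to evaluate the safety and efficacy of Brexpiprazole in adults with borderline personality disorder (BPD". Safety is thus part of the primary objective, although the hypothesis, the primary outcome and the sample size all concern efficacy.

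On how safety is measured, the Safety Assessments section begins: "Safety and tolerability will be assessed using spontaneously reported adverse events data, C-SSRS, vital signs, and by evaluating premature termination". It continues: "Safety assessments (sitting blood pressure, heart rate, adverse effects, and concomitant medications) will be documented at each visit". It ends: "Assessment of side effects will be done at each visit". The Assessments at each visit section adds: "All follow-up visits will include safety measures (adverse events, vital signs, C-SSRS), weight, BPD measures, and other psychiatric measures".

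The Risks of Brexpiprazole section names two effects as most common: weight gain, and "Inner sense of restlessness (feeling like one needs to move". Among the more serious effects it lists tardive dyskinesia, explained as uncontrollable movement. The general Risks section says that participants who notice any side effect are to get in touch with the study doctor at once.

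The Data Analysis section defines a safety set but states no method for comparing adverse events between arms.

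**The concern.** Spontaneous report is the one ascertainment method the protocol states. The later sentences in the same section say when side effects are assessed and recorded, not how. Among the many psychiatric instruments named in the protocol, none is presented as a rating of restlessness or abnormal movement, and no directed question on either is described.

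Unprompted reporting depends on the participant noticing an effect, attributing it to treatment and choosing to mention it. If some cases are lost in this way, the event count in each arm is too low and the difference between arms is likely to be too small. That matters because good tolerability is already a premise of the plan: Choice of Medication cites few side effects as a reason to choose the drug, and Sample Size uses the low adverse event rate to justify a smaller trial. A method that may miss events is a weak test of that premise, and events never elicited cannot be recovered at the analysis stage.

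**Working it through.** **1. Listed effects against stated measurement.**

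| Listed effect | Directed measurement in the protocol |
|---|---|
| Weight gain (most common) | Weight at every follow-up visit |
| Restlessness (most common) | None named |
| Uncontrollable movements (serious) | None named |

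One of the two most common effects has its own measurement and the other does not. This step needs no assumption.

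**2. The plan's own figure.** There is no safety figure to reproduce. The 40 per group in Sample Size is for the efficacy endpoint, and no effect size, standard deviation or power accompanies it. No adverse event rate is given anywhere. The steps below are therefore illustrative: 40 per arm and two-sided 0.05 come from the documents; event rates and capture fractions are my assumptions.

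**3. Effect of incomplete capture.** Let p1 and p2 be the true rates on drug and placebo, and s the fraction of cases captured, equal in both arms. The expected observed difference is s(p1 − p2). The expected risk ratio is unchanged, so the bias toward no difference applies to the difference scale and to power.

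Power = Φ[(d − 1.96·SE0)/SE1], where d is the observed difference, SE0 = √[p̄(1 − p̄)·2/40] and SE1 = √[(p1(1 − p1) + p2(1 − p2))/40], using the observed rates.

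- Full capture, 20% vs 5%: d = 0.15, p̄ = 0.125, SE0 = 0.0740, SE1 = 0.0720. Power = Φ(0.07) = 0.53.
- Half capture, 10% vs 2.5%: d = 0.075, p̄ = 0.0625, SE0 = 0.0541, SE1 = 0.0535. Power = Φ(−0.58) = 0.28.

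| True rates | Power, s = 1 | s = 0.75 | s = 0.5 | Expected drug-arm cases (40·s·p1) |
|---|---|---|---|---|
| 10% vs 3% | 0.24 | 0.19 | 0.14 | 4, 3, 2 |
| 15% vs 5% | 0.32 | 0.24 | 0.17 | 6, 4.5, 3 |
| 20% vs 5% | 0.53 | 0.41 | 0.28 | 8, 6, 4 |
| 30% vs 5% | 0.85 | 0.71 | 0.51 | 12, 9, 6 |

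**4. Chance of seeing no case at all on drug.** This is (1 − s·p1)^40. With a true rate of 15%: 0.85^40 = 0.15% with full capture, 0.925^40 = 4.4% with half, and 0.95^40 = 12.9% with one third.

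**5. Could directed questions make matters worse?** They may also pick up restlessness unrelated to treatment. Suppose they capture every true case (20% vs 5%) but add 10 points of background to both arms, giving 30% vs 15%: p̄ = 0.225, SE0 = 0.0934, SE1 = 0.0919, power = Φ(−0.36) = 0.36. With 20 points added, 40% vs 25%: p̄ = 0.325, SE0 = 0.1047, SE1 = 0.1034, power = Φ(−0.53) = 0.30. Both remain above the 0.28 for half capture in step 3. A baseline item would help to separate pre-existing restlessness from new cases.

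**The case against.** The strongest reply is that the protocol does provide for side-effect assessment at each visit, and says so more than once. That does not establish unprompted reporting alone; the method may simply be unstated. Participants are told to contact the study doctor about side effects, the consent pages are not available for review, and the protocol describes restlessness in lay terms. Stopping early counts as a safety measure, so intolerance severe enough to end treatment has a second route into the data. Every rate in the working is assumed, and even at one-third capture of a 15% rate there is about an 87% chance (1 − 0.129) of at least one reported case.

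Most of this stands, and it limits the point. A reader might infer that staff never ask about side effects; the documents do not show that. A reader might also infer that under-counting is certain; there are no capture data to prove it or to size it. What the reply does not remove is that the one stated method is the weaker one and the per-visit assessment has no content. If active questioning is intended, the section's statements need reconciling; if it is not, the method needs changing. Either way the text has to change.

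A further inference is that unrecognised restlessness would be scored as borderline symptoms and so mask benefit on the Zanarini scale. This is plausible, since the Background section describes the disorder by mood instability and impulsive behavior. But the documents give no item content that shows the overlap, any such bias would run against the drug, and a side-effect checklist would not tell raters how to score the scale. I do not rest the point on it.

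A last objection is fair: directed questions on restlessness may hint at allocation to a rater who also scores efficacy, and the protocol does not separate the two roles.

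**Conclusion.** The concern holds in a limited form. Safety is part of the primary objective, spontaneous report is the only stated way of finding adverse events, and no question or rating is directed at restlessness or abnormal movement. These effects may be under-counted, and the difference between arms may then be biased toward zero.

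The size is unknown from the documents. In the illustration, half capture halves the expected difference and lowers power from 0.53 to 0.28 at true rates of 20% and 5%; across the rates tried, power falls from 0.24–0.85 to 0.14–0.51. These figures assume equal capture in both arms and no false reports. They also show that 40 per arm gives limited power for a safety comparison at most of these rates even with full capture, so better elicitation improves the safety data without making the trial a powered safety study.

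It would be too strong to treat safety as a co-primary endpoint of equal weight, because the hypothesis, primary outcome and sample size are about efficacy. This is a change that should be made, not a flaw that invalidates the trial.

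**What to change.** In Safety Assessments, reconcile the opening sentence with the per-visit assessment, and replace the reference to spontaneous reports with wording such as:

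> At baseline and at every visit, in person or by video, and after the efficacy ratings are complete, staff will ask one open question about any new problem and then a short fixed set of directed items. The items cover listed effects that a participant can report or staff can observe, including restlessness and abnormal movements, each with a severity grade. Wording and order are identical in both arms.

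In Data Analysis, state that counts from the open question and unprompted reports will be shown separately from counts from the directed items, by arm, with denominators and a confidence interval for the difference. Keeping the two apart preserves comparability with trials that used spontaneous report.

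Listed effects that cannot be elicited by asking or observing, such as laboratory findings, do not belong in the directed items.

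**Cost.** An estimated 2–3 minutes per visit. With baseline plus 7 or 8 visits to week 12, depending on which visit schedule in the protocol applies, that is about 16 (2 × 8) to 27 (3 × 9) minutes per participant. Reported event counts will rise in both arms, so tolerability will look somewhat less favourable. There is a small risk of hinting at allocation; asking after the efficacy ratings limits it within a visit but does not remove it across visits.

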### **Data Analysis**

Data analysis will involve all visits during the 12-week double-blind treatment phase (up until week 12). Data from the tapering phase (weeks 12-13), although collected, will not be included for purposes of the primary goal of this study.

All enrolled subjects will be included in the analyses of baseline demographics and safety according to an intent-to-treat (ITT) principle. For statistical analysis, the full-analysis set will be defined as all participants who took at least 1 dose of the study drug and had at least 1 post-baseline primary efficacy assessment. The safety-analysis set will be defined as all randomized participants who took at least 1 dose of the study drug and completed at least 1 follow-up safety assessment.

The statistical model will be a linear mixed-effects regression model (LME) that includes terms for treatment group, time, and treatment-by-time interaction. The analyses will run using the nlme package on R for Windows (R Foundation, Vienna, Austria; <http://www.r-project.org>). Literature suggests LME without imputation may provide more accurate and stable results than LME models using fixed and multiple imputation methods for handling missing data, so no imputation will be undertaken for missing data. All tests of hypotheses will be performed using a two-sided significance level of 0.05.

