### **Sample Size**

The sample size was calculated for the primary endpoint of change from baseline. Assuming a similar magnitude of effect seen in other studies of medications for BPD, it was determined that 40 participants would be needed in each treatment group to detect a difference with an overall 5% type-I error risk. Given the particularly low rates of adverse events reported with Brexpiprazole, as well as its more positive side effect profile in terms of sexual side effects, we expect few drop-outs from the study and therefore a smaller sample is needed.

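### Weight gain is the first-listed common drug effect and weight is scheduled at every visit, but the safety measures omit weight and no between-arm safety analysis is stated

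*Combined protocol and SAP*

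**What the plan says.** - **Objective.** Safety and efficacy stand together in the primary objective.
- **Risks of Brexpiprazole.** Under the lead-in "The most common side effects associated with Brexpiprazole include" there are two entries. Weight gain is the first and restlessness the second.
- **Assessments at each visit.** Weight is taken at baseline, named apart from vital signs. For later visits the section says: "All follow-up visits will include safety measures (adverse events, vital signs, C-SSRS), weight, BPD measures, and other psychiatric measures". Weight again stands apart from vital signs, and outside the bracket that spells out the safety measures. The section also permits video visits and does not say how weight is then obtained.
- **Safety Assessments.** The defining sentence is "Safety and tolerability will be assessed using spontaneously reported adverse events data, C-SSRS, vital signs, and by evaluating premature termination". A second list, of items documented at each visit, names sitting blood pressure, heart rate, adverse effects and concomitant medications. Neither list contains weight. The section also provides for side effects to be assessed at each visit.
- **Efficacy evaluation.** Weight is not among the efficacy measures.
- **Data Analysis.** A safety-analysis set is defined: randomized, at least one dose, at least one follow-up safety assessment. The model is described as follows: "The statistical model will be a linear mixed-effects regression model (LME) that includes terms for treatment group, time, and treatment-by-time interaction". That description names no outcome. No safety variable is tied to the model or to any other comparison of the arms.

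**The concern.** Weight will be collected repeatedly, but no sentence says what will be done with it. It is neither a listed safety measure nor an efficacy measure, and no estimate is planned for it. The routes by which a weight effect could reach the safety conclusion are those that Safety Assessments names, chiefly adverse-event reports.

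A report is a coarse version of a weight change. The gain must be large enough to be noticed, someone must record it, and the result is a yes or no. With 40 per arm, such counts may fail to separate the arms where the mean change would. The trial could then report no weight signal for a known common effect while its own measurements show one. Without prespecification, it would also be open whether the weight data are reported at all once results are known.

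**Working it through.** **1. Is weight covered under another name?** The only candidate is vital signs. Assessments at each visit lists weight and vital signs as separate items both at baseline and at follow-up, and Safety Assessments itemises blood pressure and heart rate. Vital signs therefore does not clearly include weight.

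**2. Inputs from the documents.** Sample size: "40 participants would be needed in each treatment group to detect a difference with an overall 5% type-I error risk". Level: "All tests of hypotheses will be performed using a two-sided significance level of 0.05". The 40 per arm was set for the primary efficacy endpoint and cannot be reproduced, since effect size, SD and power are not given. Solved backwards with a two-sample t-test, it corresponds to a standardized effect of 0.63 at 80% power or 0.73 at 90%. No figure is stated for weight.

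**3. Assumed inputs (not in the documents).** SD of 12-week weight change 3 or 4 kg; true difference 2 kg; placebo mean change 0; normal changes; 40 complete weights per arm. A reportable gain is at least 3 kg, of which a share r is reported, with r = 0.3, 0.6 or 1.

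**4. Measured weight: difference in mean change.**
- 95% CI half-width = t(0.975, 78) × SD × √(2/40) = 1.991 × 0.2236 × SD = 0.445 × SD. This is 1.34 kg for SD 3 and 1.78 kg for SD 4.
- Standardized difference = 2/SD. For SD 3 it is 0.667, with power 84%. For SD 4 it is 0.5, with power 60%.

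**5. The same shift seen only through reports.** Reporting probability = r × P(gain ≥ 3 kg).
- SD 3: placebo 1 − Φ(3/3) = 0.159; active 1 − Φ((3 − 2)/3) = 0.369.
- SD 4: placebo 1 − Φ(3/4) = 0.227; active 1 − Φ((3 − 2)/4) = 0.401.

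Exact power of Fisher's test, 40 per arm, two-sided 0.05:

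| SD | r | placebo | active | power, reports | power, mean change |
|---|---|---|---|---|---|
| 3 kg | 0.3 | 4.8% | 11.1% | 7% | 84% |
| 3 kg | 0.6 | 9.5% | 22.2% | 25% | 84% |
| 3 kg | 1 | 15.9% | 36.9% | 49% | 84% |
| 4 kg | 0.3 | 6.8% | 12.0% | 5% | 60% |
| 4 kg | 0.6 | 13.6% | 24.1% | 16% | 60% |
| 4 kg | 1 | 22.7% | 40.1% | 30% | 60% |

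**6. How far does this depend on the assumptions?** A wider grid was also run: SD 2 to 4 kg, difference 1 to 2 kg, threshold 2 to 5 kg, 50% or 100% reporting. Mean change had more power at every combination, but the gap varied greatly. It was small at SD 2, difference 2 kg, threshold 2 kg and full reporting (99% against 88%). It was large at SD 3, difference 2 kg, threshold 5 kg and half reporting (84% against 4%). At SD 4 and a 1 kg difference, mean change itself had only 20%.

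**7. Missing weights.** If only 32 per arm had usable weights (an assumption), the half-width would be about 1.5 kg (SD 3) or 2.0 kg (SD 4), and power for 2 kg would be 75% or 50%.

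**The case against.** A reader might infer that the whole safety half of the primary objective rests on spontaneous reports. It does not: the same sentence names the C-SSRS, vital signs and premature termination. Only the weight signal is affected.

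A reader might also infer that a gain counts only if the participant volunteers it. That is too strong. Side effects are assessed at each visit, and nothing stops staff from recording a measured gain as an adverse effect. This is why the table includes full reporting; the gap narrows but remains.

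Nor is weight singled out. No safety variable has a stated between-arm analysis, and blood sugar and cholesterol, drawn at baseline and last visit, are also missing from both safety lists. The model in Data Analysis does not exclude weight, and silence is not a decision to discard it. This stands as a limit on the wording. It does not remove the point, because a model that could be applied to weight is not a plan to apply it.

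Finally, the documents supply no SD, difference or reporting rate, and they propose no test on report counts. Fisher's test is used here only as a yardstick for how much information the counts carry. The direction of the comparison held at every combination tried, but its size is not a fact about this trial. The Study Design section calls this a pilot, and the sample was set for efficacy, so precision on any safety measure will be limited.

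**Conclusion.** The point holds in limited form. Weight is omitted from the stated safety measures although it is scheduled at every visit and weight gain is the first-listed common effect. No between-arm analysis is stated for it or for any other safety measure. As written, a weight effect reaches the safety conclusion mainly through adverse-event reports.

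Under the stated assumptions, measured weight gives 84% (SD 3) or 60% (SD 4) power for a 2 kg difference. Report counts give 7% to 25% or 5% to 16% at 30% to 60% reporting, and 49% or 30% if every gain of at least 3 kg is reported. The half-width of about 1.3 to 1.8 kg matters most, since it makes the estimate informative whether or not a test is significant.

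The documents do not support calling the reports far less sensitive without qualification, because that rests on the assumed figures. The efficacy result is unaffected. The change should be made because it is cheap and bears on part of the primary objective.

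**What to change.** 1. In Safety Assessments, add weight to the safety and tolerability measures.
2. In Data Analysis, state that change from baseline in weight, blood pressure and heart rate will be analysed in the safety-analysis set already defined there. Use the planned mixed model (treatment, time, treatment-by-time) with the baseline value added as a covariate, and all available visits to week 12. The covariate is an addition to the stated model and should be written in as such.
3. Report the week-12 between-arm difference for each measure with its 95% CI, and interpret it by estimate and interval.

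The cost is a few sentences and a few model runs on measurements already scheduled, with no extra visits, procedures or participants. The downside is a few more reported estimates, and wider intervals if weights are missing at online visits.

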### **Subjects**

#### *Inclusion criteria:*

- 1) Men and women age 18-65;
- 2) Primary diagnosis of BPD
- 3) Zanarini scale score of at least 9 at baseline
- 4) Ability to understand and sign the consent form.

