#### *Exclusion criteria:*

- 1) Unstable medical illness based on history or clinically significant abnormalities on baseline physical examination
- 2) Subjects with schizophrenia or bipolar I disorder
- 3) Subjects with an active substance use disorder
- 4) Current pregnancy or lactation, or inadequate contraception in women of childbearing potential
- 5) Subjects considered an immediate suicide risk based on the Columbia Suicide Severity rating Scale (C-SSRS) ([www.cssrs.columbia.edu/docs](http://www.cssrs.columbia.edu/docs))

- 6) Illegal substance use based on urine toxicology screening (excluding marijuana given the high rates of marijuana use in BPD and the lack of interaction with brexpiprazole).
- 7) Initiation of psychological interventions within 3 months of screening
- 8) Use of any new psychotropic medication started within the last 3 months prior to study initiation
- 9) Previous treatment with Brexpiprazole
- 10) Cognitive impairment that interferes with the capacity to understand and self-administer medication or provide written informed consent

Advertisements will target this study population. Interested individuals will be asked to contact a study coordinator or complete an online survey expressing interest. Individuals will then undergo a phone screen before being scheduled for a first appointment. After being screened, potential subjects will be scheduled for a first appointment in which we will confirm medical and psychiatric history, laboratory tests, and inclusion/exclusion criteria.

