### **Blinding**

Blinding is critical to the integrity of this clinical study. However, in the event of a medical emergency or pregnancy in an individual subject, in which knowledge of the investigational product is critical to the subject's management, the blind for that patient may be broken by the treating physician.

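### No pregnancy test is planned after the initial visit, although pregnancy bars entry and is a named ground for breaking the blind

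*Combined protocol and SAP*

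**What the plan says.** Exclusion criterion 4 covers "Current pregnancy or lactation, or inadequate contraception in women of childbearing potential". The population is "Men and women age 18-65", so it includes women of childbearing potential.

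The test appears in two places. Assessments at each visit puts it in the baseline list: "Urine pregnancy test (for women of childbearing years) and urine drug screen". Safety Assessments gives its timing, "Urine pregnancy tests will be performed at the initial visit", and the consequence of a positive result: "Subjects who have a positive urine pregnancy test will be excluded from the study".

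The content of later visits is also stated twice. Assessments at each visit says "All follow-up visits will include safety measures (adverse events, vital signs, C-SSRS), weight, BPD measures, and other psychiatric measures", and Safety Assessments says "Safety assessments (sitting blood pressure, heart rate, adverse effects, and concomitant medications) will be documented at each visit". Neither list contains a pregnancy test. The blood samples at the last visit are for blood sugar, glutathione and cholesterol.

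The Blinding section lets the treating physician break the blind "in the event of a medical emergency or pregnancy in an individual subject" where knowing the product is critical to that person's management.

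**The concern.** The plan treats pregnancy as serious enough to keep a woman out of the trial and to justify breaking the blind, yet it schedules no test for it once dosing has begun. One test on one day cannot find a later conception and may miss a very recent one. A participant who does not know that she is pregnant has nothing to report, so exposure could continue to the end of the taper.

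What is at stake is participant safety, and how completely the trial can describe exposure in pregnancy. The primary efficacy comparison is not at issue.

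**Working it through.** **Length of the untested period.** Treatment Duration, Visit Frequency, and Procedures gives 12 weeks of treatment and a 1-week taper: 12 + 1 = 13 weeks, which agrees with the stated total.

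**Visits in that period.** Under Study Design/Methodology, the post-baseline visits through week 12 fall at weeks 1, 2, 4, 6, 8, 10 and 12, which makes 7. Treatment Duration allows weekly visits for the first 2 to 4 weeks. If they run to week 4, week 3 is added, which makes 8. Planned pregnancy tests at these visits: 0.

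**Other routes by which a test might be done.**
- Subject Withdrawal repeats the screening instruments at an early-termination visit. This most naturally means rating scales. Read broadly, it would still cover only those who withdraw.
- The two adverse event reporting sections do not mention pregnancy.
- Assessments at each visit allows baseline and follow-up visits to be online and leaves blood samples and urine toxicology to the principal investigator's discretion. It does not say how, or whether, the pregnancy test is done remotely. For an online baseline visit, even the single test is not clearly secured.

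**Expected number of pregnancies.** The documents do not give the inputs, so these are assumptions: n women at risk, 40 to 70 of the 80 participants, and an annual rate r of 2% to 10% among women using contraception. The expected number conceived over w weeks, both arms together, is n × [1 − (1 − r)^(w/52)].

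| n | r | 12 weeks, both arms | 13 weeks, both arms | 12 weeks, brexpiprazole arm |
|---|---|---|---|---|
| 40 | 2% | 0.19 | 0.20 | 0.09 |
| 60 | 5% | 0.71 | 0.76 | 0.35 |
| 70 | 10% | 1.68 | 1.82 | 0.84 |

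For the middle row: 60 × [1 − 0.95^(12/52)] = 60 × 0.01177 = 0.71. The last column halves the 12-week figure because allocation is 1:1.

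The three values of n are 50%, 75% and 88% of 80. Nothing in the documents supports 40 as a floor. The result is proportional to n, so 20 women at risk would halve the first row. Conceptions shortly before baseline that the single test misses are not counted.

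**The case against.** Much of the opposing case is sound.

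- **Contraception is the plan's main control.** Inadequate contraception is an exclusion, so the risk is already reduced. This stands, and the assumed rates allow for it. But the criterion applies at entry, and no section re-checks it during treatment.
- **There are contacts at which a pregnancy could be reported.** A reader might infer that the plan has no means at all of learning of a pregnancy. The text does not support that: adverse events and concomitant medications are recorded at follow-up visits. What is missing is a planned test. Adverse event data are described as spontaneously reported, so this route depends on the participant knowing and saying so.
- **The Blinding section is a contingency clause.** A reader might infer that it contradicts the testing schedule. It does not. The same clause covers medical emergencies, which also become known when they occur, and providing for unblinding does not imply screening. This is an omission, not an inconsistency.
- **Known pregnancies need not be lost.** A reader might infer that pregnancy exposure will be absent from the safety results. Nothing says that a pregnancy, once known, would go unrecorded. Only undetected ones would be missing.
- **The harm is not sized.** Risks of Brexpiprazole lists no reproductive or fetal risk. The exclusion shows caution but does not measure the harm. The consent pages were not available for this review and may ask participants to report a pregnancy. That could strengthen reporting, but it would not add a test.

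**Conclusion.** The gap is real and limited. One pregnancy test is planned, at the initial visit, followed by up to 13 weeks of dosing including the taper and 7 or 8 visits through week 12 without another. Followed exactly, the plan leaves on-treatment pregnancy to the participant's own report.

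On the assumed inputs, about 0.2 to 1.7 pregnancies are expected over 12 weeks in both arms, or about 0.1 to 0.8 on brexpiprazole. The taper week raises the two-arm range only to about 0.2 to 1.8. These counts show only that the event is plausible in a trial of this size. They rest on numbers the documents do not supply and could be lower. The finding itself does not depend on them, since it follows from the stated visit content.

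The change is worth making because it is cheap and improves participant safety.

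**What to change.** 1. In Assessments at each visit and in Safety Assessments, add the existing urine pregnancy test, for women of childbearing potential, to on-treatment visits already scheduled and to the end-of-treatment or early-termination visit. The investigator should set the interval.
2. State how the test is done when the baseline or a follow-up visit is online, for example with a mailed kit.
3. Ask the sponsor to clarify what exclusion after a positive test means once a participant has been randomised. The sentence sits beside the initial-visit test and does not say whether it applies later. No clinical rule is proposed here.

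The cost is a line of text in each of the two sections, a few inexpensive kits, and mailing for online visits. No extra visits, staff or invasive procedures are needed, and the sample size and primary analysis do not change.
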